factors describing the intervention experience will be assessed. Such factors are the "dose of support" which will quantify by frequency and duration of support and "intervention characteristics" (while all NGOs provide advocacy-based support, the structural characteristics of services and the relative emphasis placed on components of support provided vary - reports of the National Audit Office and Public Accounts Committee, and conversations with NGOs, indicate considerable variability between services (9, 18).). Participant characteristics that predict outcomes will also be identified and dose-response analyses will be adjusted for their potential confounding effect.

9. Study setting

A total of six of the 12 NGOs providing government-funded advocacy interventions to survivors of trafficking in England have been purposively selected for variation in structural characteristics and service model. Participating organisations are as follows:

- 1. Ashiana
- 2. BAWSO
- 3. Hestia
- 4. Medaille Trust
- 5. Migrant Help UK
- 6. Salvation Army Accommodation Services

10. Eligibility criteria

Study 1 – Cohort Study

Inclusion criteria

To be eligible for inclusion in the study, participants must meet all inclusion criteria:

- 1. Be aged 18 years or older;
- 2. Have entered into the UK National Referral Mechanism;
- 3. Have consented to receive advocacy support from a participating non-governmental organisation (NGO);
- 4. At date of baseline interview, have received fewer than 14 days' residential advocacy support or 28 days' outreach advocacy support from any NGO through the UK National Referral Mechanism;
- 5. No longer be being exploited by their traffickers.

If the participant has undergone an age determination procedure (i.e. is age-disputed), the participant's age as confirmed by the local authority should be used.

Exclusion criteria

People will be excluded from the study if they:

1. Do not have the capacity to provide consent to participate in the studies, including because of learning disability, psychotic illnesses or severe drug or alcohol problems.

Eligibility will be assessed by trained NGO staff members referred hereafter as "NGO Researchers".

Study 2 - Qualitative study

Inclusion criteria

Survivors- To be eligible for inclusion, survivors must meet the inclusion criteria for the above cohort study and additionally have consented to participate in the qualitative study. English language proficiency is not a selection criterion.

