grounds decision prior to entry into NGO support, though this is not always the case. Individuals who have entered NGO support prior to receiving a reasonable grounds decision who then receive a negative decision are exited from support services.

A second "conclusive grounds" decision regarding an individual's claim to have been trafficked will then be made. The target for decision-making is 45 days, though in practice the decision-making period is often longer. An individual who receives a negative conclusive grounds decision is determined not to be a victim of trafficking, and is exited from support services. Individuals who receive a positive conclusive grounds decision can continue to receive NGO support services; the default support period in England and Wales is 45 days. Individuals can, however, apply to extend their access to support services by up to 6 months (renewable) via the Recovery Needs Assessment process.

Prior to intake, an Initial Assessment will be completed in order to determine eligibility, risk, and urgent needs. Individuals who lack mental capacity, who have severe drug and alcohol problems, or who are acutely mentally unwell are not supported by the NGO services. After arrival at NGO services, a Detailed Needs Based Assessment is undertaken, followed by an Individual Support Plan. The intervention is considered to commence at the initiation of the individual support planning process. The support plan is individualised but organised according to the following categories:

- 1. Secure and appropriate accommodation
- 2. Provision of subsistence payments
- 3. Access to emergency health services
- 4. Advocacy for specialist services
- 5. Assistance with criminal proceedings
- 6. Access to education for dependent school age children
- 7. Access to compensation

These categories align to the entitlements of survivors of trafficking under the Council of Europe Convention on Action Against Trafficking in Human Beings (ECAT) rather than to advocacy activity categories described by the initial programme theory.

Other concomitant care and interventions are permitted during the trial (e.g. psychological interventions); data on receipt of other health and social care services are collected (see section 12, outcomes).

12. Outcomes

Study 1 – Cohort Study

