Participants will be recruited over an 18-month period: 1st March 2020-31st August 2021. In the first month, recruitment will be restricted to a single organisation. From 1st April 2020, recruitment will roll out to the remaining sites.

The intake criteria of participating organisations are such that all clients should be eligible for participation in the study, i.e. they should meet all of the inclusion criteria and none of the exclusion criteria. Nonetheless, caseworkers will complete an eligibility screen prior to giving written and verbal information about the study to their clients during Initial Support Planning. All incoming clients will be screened for eligibility and, with the exception of clients who are screened as ineligible, all will be provided with information about the study. The written information to be provided comprises the participant information sheet and consent form. Translated copies of participant information sheets and consent forms will be available for clients who are not able to read English.

Clients will be asked to indicate whether they wish to be contacted by the NGO researcher to discuss potential participation or whether they wish to contact the NGO researcher themselves; their preference will be recorded on the eligibility screening sheet.

NGO researchers will contact clients who indicate that their preference is to be contacted directly after a minimum of 24 hours. These professionals will confirm eligibility to participate and explain the study aims and procedures; the nature of informed consent; potential risks; and any queries/concerns service users may have regarding their participation in the study. Where NGO researchers are caseworkers, they may provide information about the study to their own clients during Initial Support Planning, but they may not re-contact clients to determine eligibility and intention to participate in the study, take informed consent, or administer research interviews.

Clients who decline to enter the study will be asked if their basic socio-demographic characteristics can be collected anonymously to determine whether there are differences between participants and non-participants. Clients intending to participate in the study will be asked to agree a date for the T1 interview.

Study 2 - Qualitative study

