17. Blinding

There is no blinding of participants, providers, outcome assessors, or analysts.

18. Data collection methods

18a Personnel

To minimise participant burden and facilitate engagement:

- NGO caseworkers will screen incoming clients for eligibility and provide a verbal summary and written information (participant information sheet and consent form) about the study.
- NGO researchers will, after a minimum of 24 hours, confirm eligibility to participate and study information and schedule T1 interview for those intending to participate.
- NGO researchers will take informed consent and administer the T1 questionnaire and T2 questionnaire.

The PI/post-doctoral researcher will visit participating organisations to provide training to NGO researchers to ensure quality and consistency of administration; additional training will be provided as required, for example if new caseworkers are recruited or if problems of questionnaire administration or completion are identified. Fortnightly calls will be made to sites by a post-doctoral researcher to monitor recruitment and completion of questionnaires and enquire about any difficulties with recruitment or administration of questionnaires.

To minimise burden on participating organisations:

- The KCL researcher will administer T3 questionnaires
- The KCL researcher will administer T2 questionnaires to participants who leave the recruiting organisation, e.g. because they voluntarily withdraw from NRM support, because NRM support is withdrawn following a negative reasonable or conclusive grounds decision, or because they are moved to a new NRM support service.
- The KCL researcher will conduct interviews with survivors and staff for the qualitative study.
- Data entry for the cohort study will be completed at KCL under the supervision of the post-doctoral researcher.

To facilitate participation by clients who do are not proficient in English:

• Independent and professionally qualified interpreters will be available to interpret during the provision of information about the study, informed consent processes, and questionnaire administration.

18b Mode

Interviews may be scheduled to take place either face-to-face or by telephone; the mode of interview will be recorded.

18c Interpretation

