Participant Identification Numbers (PINs) are assigned to cohort study participants via the MACRO database after the T1 interview has been completed/terminated. After completing the interview, the NGO researcher should log into the MACRO database and complete the participant Registration Form. Completion of this form automatically generates a PIN. The PIN should be written in ink at the top of all sheets in the questionnaire pack and the questionnaire pack then securely stored as detailed below.

18i Retention

People recruited to the research may (a) drop out of the support programme; (b) drop out of

the research; (c) both. We will seek to retain participants in the research if they drop out of the support programme. As per section 16a, the KCL researcher will administer T2 and T3 questionnaires to participants who leave the recruiting organisation.

We will use several strategies to reduce drop out from the research based on the experience of the applicants and collaborators in conducting evaluations of complex interventions. These include:

- Asking participants to complete a contact details information sheet at baseline, including a contact telephone number and (if applicable) email address, plus a contact telephone number for a person they trust. The participant information sheet explains that we request the details of a trusted contact in case we are unable to get in touch with them at follow-up.
- Upon completion of T2, provision of a business card with the details of the Study Manager plus a stamped addressed envelope in case of change in contact details.
- Upon receipt of information following T2, the Study Manager will telephone the participant to introduce themselves, thank them for participating to date, and to let them know they will be in touch with them in three months' time to complete the final questionnaire. This additionally provides an opportunity to recheck contact details.
- Providing flexible follow-up appointments (see section 13 for details of data collection windows):
- Providing expenses to cover travel to appointments if required;
- Sending text message reminders at interview 1 week and 1 day prior to follow-up appointments;
- Maintaining contact between data collection points (e.g. thank you cards, newsletters);
- Providing multi-use shopping vouchers thank participants for their time.

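### At T3 the interviewer changes for the whole cohort from NGO staff to the university researcher, so the T1–T3 mean change cannot be separated from a change of interviewer type

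*Protocol*

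**What the plan says.** Section 18a (Personnel) divides the interviews by visit. For the first two visits: "NGO researchers will take informed consent and administer the T1 questionnaire and T2 questionnaire". For the third, without restriction to a subgroup: "The KCL researcher will administer T3 questionnaires". There is one exception at T2: "The KCL researcher will administer T2 questionnaires to participants who leave the recruiting organisation". Section 18i repeats that rule for leavers at both follow-up visits.

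The NGO researchers belong to the organisations whose support is being evaluated; section 10 introduces them with the words "Eligibility will be assessed by trained NGO staff members referred hereafter as" NGO Researchers. Section 15 limits those who are also caseworkers. With respect to their own clients, "they may not re-contact clients to determine eligibility and intention to participate in the study, take informed consent, or administer research interviews".

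Section 18g makes the cohort questionnaire interviewer-administered rather than self-completed. Section 17 states that nobody is blinded, and section 8(b) explains why there is no control group. On mode, section 18b says: "Interviews may be scheduled to take place either face-to-face or by telephone; the mode of interview will be recorded".

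Sections 8(a) and 12 make CORE-OM at T2 versus T1 the primary outcome and CORE-OM at T3 a secondary one. Section 20a, however, describes the paired test as one of mean change over the 6-month study period, that is, T1 to T3. Section 20b plans one sensitivity parameter: the mean change that a hypothetical control group would have shown, drawn from literature on people waiting for a programme.

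**The concern.** In a controlled trial, a shift in answers caused by who is asking would tend to cancel between arms. Here it passes in full into the pre–post difference. Every participant's T1 answers are given to NGO staff and every participant's T3 answers to the university researcher, so no covariate model fitted within this cohort can separate the two sources of change.

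At stake is the reading of the 6-month CORE-OM change and of the other interviewer-administered T3 outcomes as change during support. For participants who stay with the NGO, the T2–T3 course is exposed in the same way and could bend because the interviewer changed. The consistency training in section 18a is described for NGO researchers. No step is described for aligning NGO and university interviewers, and section 20 uses neither interviewer type nor mode.

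**Working it through.** **Who interviews whom (sections 18a and 18i)**

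| Participant | T1 | T2 | T3 |
|---|---|---|---|
| Stays with recruiting NGO | NGO | NGO | KCL |
| Leaves before T2 | NGO | KCL | KCL |

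T1–T3 crosses from NGO to KCL in both rows. T1–T2 is like-for-like only in the first row, and T2–T3 only in the second.

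**The plan's own figures (section 14).** Inputs: 450 recruited, 25% loss and then a further 25%, SD 18, two-sided 5%, d = 0.18 at T2 and 0.20 at T3.

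- Retained: 450 × 0.75 = 337.5 at T2; 337.5 × 0.75 = 253 at T3. This agrees with the stated 250.
- Detectable differences: 0.18 × 18 = 3.24 and 0.20 × 18 = 3.6, as stated.
- Power from the noncentral t distribution: 0.909 at T2 (n = 337); 0.883 to 0.887 at T3 (n = 250 to 253). This is within 2 points of the stated 90%.

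**Effect of an assumed interviewer shift on T1–T3.** Write the observed mean change as D = true change + s, where s is the shift. With no true change, the rejection rate is that of a noncentral t with n − 1 degrees of freedom and noncentrality (s/18) × √n. With n = 253:

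| Assumed s (CORE-OM points) | s/18 | Significant T1–T3 results |
|---|---|---|
| 0.5 | 0.03 | 7% |
| 1.0 | 0.06 | 14% |
| 1.8 | 0.10 | 35% |
| 2.0 | 0.11 | 42% |
| 3.0 | 0.17 | 75% |
| 3.6 | 0.20 | 89% |

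The smallest observed mean change that reaches p < 0.05 is t(0.975, 252) × 18/√253 = 2.23 points.

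In the other direction, with a true improvement of 3.6 and n = 250, an opposing shift of 1 or 2 points cuts power from 88% to 62% or 29%.

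**Tipping point.** If the observed improvement were exactly 3.6 points, its confidence limit nearer zero would be 3.6 − 2.23 = 1.37. A combined allowance of about 1.4 points for natural change and interviewer shift would then remove significance.

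**Dose-response slopes.** If change = a + b × dose + s with the same s for everyone, then change = (a + s) + b × dose. The intercept moves and b does not.

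**The case against.** The strongest reply is that this is a limitation of secondary mean changes in a study that calls itself exploratory. The declared primary outcome is T1–T2, where participants who stay have the same interviewer type twice. CORE-OM items are fixed, asked in a set order and answered by the participant, with no interviewer rating described. The causal argument rests largely on dose-response, which a common shift leaves unbiased. The change of interviewer is a reasoned choice to spare the NGOs work. All of this stands, and it limits the point to T1–T3 mean changes and, for those who stay, T2–T3 mean changes.

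A second reply is that the section 20b parameter already does the arithmetic, because an additive shift is subtracted in the same way as a hypothetical control change. That is correct and makes the remedy cheap. But the planned range comes from waiting-control literature, so it reflects natural change and not a change in measurement.

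Third, the 89% is simply the study's own power for 3.6 points restated, and any bias of that size would give it. That is also correct; the table shows sensitivity and does not estimate a bias.

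A reader might also infer that the protocol supplies a motive for answering differently by listener, since section 11 says that people with a positive conclusive grounds decision can "apply to extend their access to support services by up to 6 months (renewable) via the Recovery Needs Assessment process". The text does not support this. It describes a route to longer support and does not connect research answers to that assessment. Section 15 keeps caseworkers from interviewing their own clients, and section 27 has participants told that responses are confidential and that taking part does not affect their service. Courtesy towards the NGO could equally push answers the other way.

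**Conclusion.** The point holds in a limited form. Section 18a fixes a complete confounding of interviewer type with time for T1–T3, in a study with no control group to absorb it and with a 6-month change as the test named in section 20a. The T1–T3 mean change therefore cannot be read as change during support alone.

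The size and direction of any shift are unknown, and the protocol states no mechanism. The illustration (35% and 89% significant results for assumed shifts of 1.8 and 3.6 points) rests on n = 253, no true change, and the protocol's SD of 18 taken as the SD of change.

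Two wider readings are not supported. The primary T1–T2 contrast is not compromised for the whole cohort; only those interviewed by the university researcher at T2 change interviewer there. Nor are the dose-response slopes on T1–T3 change biased by a shift that is the same for everyone.

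**What to change.** 1. In section 20, name T1–T2 among participants interviewed by NGO researchers at both visits as the like-for-like comparison. State that T1–T3 mean changes and, for those who stay, T2–T3 mean changes include a change of interviewer and are not to be read as change during support alone.
2. Extend the section 20b sensitivity parameter for T1–T3 so that its range also covers an additive interviewer shift, on top of the hypothetical-control change. The range must be assumed; −3.6 to +3.6 CORE-OM points would match the protocol's own detectable difference. Report the combined shift at which the conclusion changes.
3. Use the interview mode already recorded to report T1–T3 change in participants whose mode did not change. Do not make constant mode a scheduling rule, since that would work against the flexible appointments in section 18i and the fixed windows in section 13.

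The cost is some added text and a few lines of analysis within a framework already planned, with no extra interviews or staff. T3 conclusions become more cautious. The like-for-like T1–T2 group is also selected, because it consists of people who stayed with the NGO; it should sit beside the full primary analysis, not replace it.

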The "dose of the support received" will be quantified (e.g. duration in terms of session length, frequency, and the period over which sessions are received; structural and service characteristics NGOs) and change scores will be regressed on this dose. Possible confounders of the dose-response relationship will be identified by testing whether any baseline participant characteristics (e.g. gender, immigration status) predict change over time. Any such potential confounders will then be adjusted for in a second step which regresses the change changes on the dose variable and the putative confounders.

These analyses (which do not include a control group) are based on the assumption that a control group would not exhibit any change over the intervention period. In order to assess the

impact of departures from this assumption on the evaluation of the advocacy support intervention sensitivity analyses will be conducted. Literature evidence will be used to generate a possible distribution of mean outcome change in a hypothetical control group of eligible trafficked woman waiting to start the support program (37); and will then include such sensitivity parameters in our analyses models to study their impact on the estimation of the prepost effect.

20c Methods for handling missing data

In the case of missing data in the CORE-OM outcomes, putative baseline confounders, or process variables, multiple imputation (MI) will be used to ensure that the analyses remain valid under an appropriate missing at random assumption. This will enable us to (multiply) impute realistic outcome patterns including allowing for process variables such as discontinuation of advocacy support to drive loss-to follow-up.

21. Economic evaluation

An exploratory analysis of service use, costs and effects before and after intervention will be undertaken with the results presented using a cost consequences framework, which is recommended for the evaluation of complex interventions that have multiple effects (38). This work will be used to support the generation of recommendations for future research and the development and testing of economic measures appropriate for this population. Specific objectives will include the following:

- 1. Calculate the cost of the advocacy interventions taking a micro-costing (bottom-up) approach (38).

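### The T1–T2 dose-response slope is open to bias from who interviews leavers and from negative NRM decisions, and the baseline-only adjustment in 20b can address neither

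*Protocol*

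**What the plan says.** **Who interviews.** Section 18a says "NGO researchers will take informed consent and administer the T1 questionnaire and T2 questionnaire". The exception is that "The KCL researcher will administer T2 questionnaires to participants who leave the recruiting organisation". Three examples of leaving follow: voluntary withdrawal from support, withdrawal of support ("because NRM support is withdrawn following a negative reasonable or conclusive grounds decision"), and transfer ("or because they are moved to a new NRM support service"). At the last time point the interviewer is the same for all: "The KCL researcher will administer T3 questionnaires".

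**How the outcome is taken.** The questionnaire is administered by the researcher (section 18g). Nobody is blinded, outcome assessors included (section 17).

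**The decision.** Under section 11 a Single Competent Authority, not the NGO, decides. A person with a negative conclusive grounds decision "is determined not to be a victim of trafficking, and is exited from support services". The target is 45 days, and it is often exceeded. T2 falls at 90 days (section 13), so some decisions can precede it.

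**The analysis.** Section 20b regresses change scores on dose, which includes the period over which sessions were received. Confounders are found by "testing whether any baseline participant characteristics" predict change. Discontinuation of support appears only in 20c, as an input to multiple imputation.

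**Its role.** Section 8(b) offers the dose-response as support for a causal interpretation in the absence of controls.

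**The concern.** Whether a participant has left the recruiting NGO determines who conducts the T2 interview. For some leavers it also goes with a shorter period of support and a negative decision. A regression of T1–T2 change on dose therefore mixes three things: any effect of support, any difference between reporting distress to NGO staff and to a university researcher, and any direct effect of the decision on distress.

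The last two arise after baseline, so a rule that searches baseline characteristics cannot select them. Multiple imputation does not help either. It deals with people who were not observed, not with confounding or differential measurement among those who were.

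What is at stake is the study's main internal argument for causation. The sensitivity analysis in 20b for a hypothetical control group concerns the mean pre-post change and leaves the dose slope untouched.

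**Working it through.** **1. The plan's own figures (section 14).** 450 × 0.75 = 337.5 at T2, and 337.5 × 0.75 = 253 at T3. The detectable d is (1.960 + 1.282)/√n:
- T2: 3.242/√337 = 0.177, and × 18 = 3.18 points.
- T3: 3.242/√253 = 0.204, and × 18 = 3.67 points.

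These agree with the stated 0.18 and 0.20 (3.2 and 3.6 points). They concern the paired test. The protocol gives no figure for the dose slope or for the share of leavers.

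**2. Can the stated rule reach the problem?** The two variables are T2 interviewer and decision status by T2. Both arise after baseline, and 20b searches baseline characteristics only. So it cannot.

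**3. Expected slope when the true dose effect is zero.** These inputs are assumptions: share of leavers p; dose 1 for stayers and 0.5 for leavers, plus other variation with SD 0.4; change score SD 1; leavers' change shifted by s (positive means worse). Then

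slope = −0.5·p(1−p)·s / [0.25·p(1−p) + 0.16].

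For p = 0.25, p(1−p) = 0.1875, and the slope is −0.09375·s/0.206875 = −0.453·s. Shifts of 0.2, 0.3 and 0.5 SD give −0.09, −0.14 and −0.23 SD per unit of dose, all spurious.

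**4. How often that is falsely significant.** Simulated with n = 337, ordinary least squares and a two-sided 5% test. The nominal rate in the direction of benefit is 2.5%.

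| 25% leavers | s = 0.2 | s = 0.3 | s = 0.5 |
|---|---|---|---|
| All leavers have half dose and the full shift | about 11% | about 20% | about 46% |
| One third are transfers with full dose and no shift | about 9% | about 14% | about 30% |
| Leavers split equally by reason; only negative-decision leavers shift | about 5% | about 6% | about 10% |

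With 15% leavers the first row falls to about 8%, 12% and 25%. With s = −0.3 (leavers have improved), 25% leavers and the first row's set-up, false harm appears in about 20% of studies and false benefit almost never.

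**5. A second set-up.** Dose is in months: leavers 0.5 to 2.5, stayers about 3. The SD of change is 18 and leavers are 10% to 30%. If leavers score 1.8, 3.6 or 7.2 CORE-OM points worse, false benefit occurs in 6–11%, 15–31% and 43–84% of runs. If they score 3.6 points better, false harm occurs in 14–30%.

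In the first-row set-up, adding a leaver term to the model returns the rate to about 2.5% in each direction. That is no evidence that the adjustment works in practice, because the data were generated with exactly that term.

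**The case against.** A reader might infer that the dose-response is biased towards benefit, that leavers often have a negative decision, and that leavers as a group get a lower dose. The protocol supports none of these.

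- **Direction.** Nothing gives the sign of an NGO-versus-KCL interviewer effect or says that a negative decision raises distress. Voluntary leavers may go because they feel better, which would push the slope the other way.
- **Frequency.** A negative decision is one of three examples, with no rate. Section 11 says conclusive decisions are often slow and that a positive reasonable grounds decision ordinarily precedes entry to support.
- **Dose.** Transferred participants go on receiving support, and dose also includes session length and frequency.

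Other points on that side:

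- **End point.** 20b speaks of change over the intervention period without naming T2, and 20a refers to 6 months. On T1–T3 change the interviewer does not differ between stayers and leavers.
- **Safeguards.** Section 15 bars NGO researchers who are caseworkers from interviewing their own clients. Section 18a provides training and fortnightly calls.
- **Place in the plan.** The study is exploratory, and sensitivity analyses commonly sit in an SAP, which is not shown.

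The first three points stand, so the claim must be limited to a slope that can be biased. The end-point argument confines the interviewer mechanism to T2, which is the primary time point; the decision mechanism remains at T3. The safeguards may narrow the interviewer difference, but they leave stayers with NGO staff and leavers with the university. The last argument would excuse silence, but 20b is not silent: it states how confounders are chosen, and that rule excludes both variables.

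**Conclusion.** The point holds in limited form. As written, the T1–T2 dose-response is open to confounding by the reason for leaving and to differential measurement by interviewer, and the stated adjustment can remove neither. A spurious benefit is plausible but not established.

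With 25% leavers, the illustrative rate of false benefit runs from about 5% to 46% against 2.5% nominal. It turns into false harm if leavers have improved. Those figures rest on an assumed leaver share, shift, dose gap and share of transfers, none of which the protocol gives. They show that the bias could matter, not how large it will be. Because even the sign is unknown, a check fixed in advance is worth more than a judgement made after the results. This is a cheap improvement and does not invalidate the design.

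**What to change.** In section 20b, keep the planned dose-response model and add:

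1. A pre-specified sensitivity analysis on T1–T2 change with terms for NRM decision status by follow-up (pending, positive, negative) and for T2 interviewer (NGO or KCL).
2. The same dose-response on T1–T3 change, where the KCL researcher interviews everyone, keeping the decision term because that confounding remains.
3. A statement that, if the slopes differ materially, the dose-response will not be read as support for a causal effect.

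Confirm that interviewer type and decision status are captured. Section 13 lists a Status Form without its contents, and section 12 describes the NGO records as type, frequency and duration of support. If either item is missing, add it.

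**Cost.** No visits or procedures change. The interval for the dose slope widens, and the T1–T3 repeat rests on about 253 people rather than 337. Leaving is partly low dose itself, so the adjusted model may over-adjust; that is why it should accompany the planned model, not replace it. Up to two extra fields may need recording.
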